4.0 TREATMENT PLAN

4.1 Overview

Treatment will be administered on an outpatient basis. Patients will first be treated one time with liver directed therapy, Therasphere® (Y-90), following institutional procedures**. During screening, each patient will undergo an angiogram in interventional radiology to determine the appropriate Y-90 dose. Within 7-14 days, patients will begin treatment with intravenous nivolumab as maintenance either at 80mg (first 3 patients in Phase I) or 240mg (Phase Ib if MTD) over 30 minutes (-5 minutes / +15 minutes) every 2 weeks (Day 1 & 15 of each cycle; 1 cycle = 28 days).

After study registration, the patient will proceed to receiving Y-90 per the standard of care procedures listed in section 8.1. Y-90 administration is normally planned around 7 days from the angiogram, so registration should be planned accordingly. After completion of Y-90, patients will have 1-2 weeks recovery time prior to proceeding with nivolumab administration (4 weeks if necessary). This window allows for recovery from generalized fatigue. Study drug nivolumab will continue until disease progression or withdrawal of treatment by patient.

*** Repeat therapy to the treated lesion or additional untreated lesions may be warranted. If a patient requires additional Y-90 after starting nivolumab treatment, it may be given once approval from the interventional radiologist and treating physician has been confirmed. In such cases, nivolumab should be held for ≥ 7 days prior to administering Y-90. Nivolumab can be resumed at least 7 days after receiving additional Y-90, but can be delayed for up to 4 weeks if needed.*

4.2 Treatment Administration

4.2.1 Theraspheres® (Yttrium-90)

Institutional Standard of Care TheraSphere Treatment Procedure:

The calculated dose of radiation to be delivered to the targeted lesion will be calculated by a medical nuclear physicist in Interventional Radiology ([name]) during the screening angiogram. Once the required dose of Y-90 is determined, it is ordered from the manufacturer. It is recommended the time lapse between work up for Y-90 (angiogram) and the treatment session should not exceed 2-3 weeks.

Please see section 8.1.6 for specific details of Y-90 administration. Patients are observed for 2-6 hours post procedure prior to discharge. Patients will be evaluated within 14 days after y-90 therapy to assess for side effects, tolerability

NU Study Number: NU 16101
BMS Study Number: CA 209-615

of therapy and laboratory abnormalities. By 12 days post therapy (4 half-lives of Y-90), the radioactivity of Y-90 has significantly decayed. Tumor response is evaluated radiographically 21-28 days post therapy. Maximal therapeutic effect may only become apparent 3 months post therapy.

Based on follow-up imaging, repeat therapy to the treated lesion or additional untreated lesions may be warranted, barring minimal complications with the first session. Radiographic evidence of progression of disease following up to 2 treatments (to the same targeted lesion) of Y-90 may warrant alternative ablative or systemic therapies. These subjects would be considered treatment failures and would be terminated from the study. On the other hand, an incomplete response or recurrent disease may call for additional therapy.

4.2.2 Nivolumab

For the first 3 patients in Phase I, nivolumab will be administered at 80mg as an intravenous infusion over approximately 30 minutes (-5 minutes / +15 minutes) every 2 weeks (Day 1 & 15 of each cycle) until disease progression or intolerable toxicity.

Dose escalation to 240mg will be determined in the standard 3+3 fashion (detailed in section 4.3). All patients in Phase Ib will be treated at 240mg IV nivolumab if determined to be the MTD. Treatment will begin 7-14 days after Y-90 administration. Patients should have recovered from any side effects resulting from Y-90 treatment (to ≤G1 or baseline). If a patient is still experiencing side effects 14 days after Y-90 treatment, the patient’s nivolumab treatment may be delayed by up to 14 additional days at the physician’s discretion (maximum 4-week delay). Scans will need to be performed 21-28 days after Y-90 administration, and will fall during Cycle 1 of nivolumab. If a patient is not able to start nivolumab treatment within 4 weeks (28 days), the patient should come off study and be replaced.

Subjects may be dosed no less than 12 days from the previous dose. There are no pre-medications recommended for nivolumab on the first cycle. If an acute infusion reaction is noted, subjects should be managed according to Section 4.2.4.

Treatment will be administered on an outpatient basis. Reported adverse events and potential risks are described below. No investigational or commercial agents or therapies other than those described below may be administered with the intent to treat the patient’s malignancy.

4.3 Phase I Dose Escalation Scheme

In this phase 1/1b pilot study, the dose escalation component will be for nivolumab, starting at a dose of 80mg. Please see the table in statistical section for dose adjustments.

Phase I Dose Escalation Plan based on 3+3 design:

Dose Level	Nivolumab
1	80mg IV every 2 weeks
2	240mg IV every 2 weeks

NU Study Number: NU 16101
BMS Study Number: CA 209-615

A standard “3+3” dose escalation design will be utilized. Initially, 3 patients will be enrolled at the starting dose (level 1), after which enrollment will be temporarily suspended until all 3 patients complete the DLT evaluation period (defined as cycle 1 or the first 28 days of treatment). Once all 3 patients complete the DLT period and toxicity data has been submitted, the Data and Safety Monitoring Committee (DSMC) will review the data and confirm the presence or absence of any DLTs (defined below). The following rules will be used at each dose level to determine whether or not to proceed to the next dose level:

- If 0 of 3 patients at a given dose level experience a DLT (defined below), then escalation will proceed to the next dose level.
- If 2 or 3 of 3 patients at a given dose level experience a DLT, then one of the following must occur:
 - If this happens at level 1, the PI will discuss with DSMC and BMS to determine the necessary outcome.
 - If this happens at level 2 or beyond, the previous level will be declared the maximum tolerated dose (MTD).
- If 1 of 3 patients at a given dose level experiences a DLT, then an additional 3 slots will be added (for a total of 6 patients at that level):
 - If 1 of 6 total experiences a DLT, then escalation will proceed to the next level.
 - If ≥ 2 of 6 total experience a DLT, the previous level will be declared the MTD.

NOTE: Whichever dose level is declared the MTD must have 6 total patients treated at that level. For example, if 3 patients are treated at level 2 and 0 patients experience DLT, escalation would then proceed to level 3. However, if ≥ 2 patients at level 3 experience DLT, enrollment to level 2 would need to be re-opened to enroll an additional 3 patients at that level (with 0 or 1 DLT observed in 6 total patients) in order to declare level 2 the MTD.

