2.0 OBJECTIVES & ENDPOINTS

2.1 Primary Objectives & Endpoints

- 2.1.1 Phase I:** To identify maximum tolerated dose (MTD) of nivolumab for combination treatment of nivolumab and Y-90 in patients with advanced hepatocellular carcinoma. The MTD will be defined as the highest dose that causes dose limiting toxicities (DLTs) in <2 of 6 patients.
- 2.1.2 Phase Ib:** To evaluate the proportion of patients with objective response rate (ORR, according to RECIST criteria version 1.1) to the combination treatment of nivolumab with Y-90.

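### In section 4.3, two or more DLTs in six patients at dose level 1 makes a level that does not exist the MTD

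*Combined protocol and SAP*

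**What the plan says.** Section 4.3 states that "the dose escalation component will be for nivolumab, starting at a dose of 80mg". Its table has two rows: level 1 at 80 mg and level 2 at 240 mg, each every 2 weeks. The scope of the rules is general: "The following rules will be used at each dose level to determine whether or not to proceed to the next dose level".

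For two or three DLTs in the first three patients, the text separates the levels. At level 1, "If this happens at level 1, the PI will discuss with DSMC and BMS to determine the necessary outcome". At level 2 or higher, the level below becomes the MTD.

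For one DLT in three, "If 1 of 3 patients at a given dose level experiences a DLT, then an additional 3 slots will be added", giving six in total. Two outcomes follow:
- With one DLT: "If 1 of 6 total experiences a DLT, then escalation will proceed to the next level".
- With two or more: "of 6 total experience a DLT, the previous level will be declared the MTD".

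Neither of these two outcomes separates level 1 from level 2.

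Two other statements constrain the result. Section 2.1.1 says: "The MTD will be defined as the highest dose that causes dose limiting toxicities (DLTs) in <2 of 6 patients". The NOTE in 4.3 says: "Whichever dose level is declared the MTD must have 6 total patients treated at that level".

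**The concern.** Level 1 is the lowest level in the table. If level 1 is expanded to six patients and two or more have a DLT, the rule names as MTD a dose that the plan does not contain. The authors saw that level 1 needs its own outcome, because they wrote one for the branch of two or three in three. They did not attach it to the branch of two or more in six.

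The MTD is the Phase I primary objective, and 10.2 sends its determination back to 4.3. At stake is whether the decision rule for that objective gives a usable answer when the starting dose of the combination proves too toxic.

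**Working it through.** **Following the rule at level 1.** Suppose one of the first three patients at 80 mg has a DLT, three more are enrolled, and at least one of those has a DLT.
1. The count is at least two in six, so the rule names the previous level. The table has no level below 1.
2. Level 1 itself cannot be the MTD, because 2.1.1 requires fewer than two DLTs in six.
3. A level that does not exist cannot have the six treated patients that the NOTE requires.
4. The consultation with the DSMC and the drug supplier is written under the other branch only.

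**Looking for a repair elsewhere.** Section 4.3 points to a table in the statistical section. Section 10, in the text available for this review, contains none. The study stopping rule in 4.9 turns on grade 4 hyperbilirubinemia in 2 of the first 5 patients or a therapy-related death, not on DLT counts.

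**How often the branch would be reached.** The plan states no probability to reproduce and no DLT rate. Appendix 5 calls a DLT at level 1 unlikely but gives no figure. The rate p at level 1 is therefore an assumption, shown over a range. Patients are treated as independent.

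- Covered branch, two or three in three: A = 3p²(1−p) + p³.
- Uncovered branch, one in three and then at least one of the next three: B = 3p(1−p)² × [1 − (1−p)³].

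At p = 0.10: A = 0.027 + 0.001 = 0.028, and B = 0.243 × 0.271 = 0.0659.

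At p = 0.20: A = 0.096 + 0.008 = 0.104, and B = 0.384 × 0.488 = 0.1874.

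| Assumed p | A, covered | B, uncovered |
|---|---|---|
| 0.05 | 0.7% | 1.9% |
| 0.10 | 2.8% | 6.6% |
| 0.20 | 10.4% | 18.7% |
| 0.30 | 21.6% | 29.0% |
| 0.40 | 35.2% | 33.9% |
| 0.50 | 50.0% | 32.8% |

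Setting A = B gives p of about 0.389. B is larger below that value and A is larger above it.

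**Re-opened level 1.** Suppose level 1 had no DLT in three, level 2 then fails, and level 1 is re-opened for three more patients. Two or three DLTs among those three give at least two in six at level 1. With rate q at level 2, the chance is (1−p)³ × [A(q) + B(q)] × A(p).
- p = 0.10, q = 0.30: 0.729 × 0.5057 × 0.028 = 1.0%.
- p = 0.20, q = 0.40: 0.512 × 0.6907 × 0.104 = 3.7%.
- p = 0.30, q = 0.50: 0.343 × 0.8281 × 0.216 = 6.1%.

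**Level 2.** No DLT in three, or one in six, tells the team to escalate. The table has no level 3, and the NOTE explains itself with a level 3 that is not in the table either.

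**The case against.** The strongest reply is that little could go wrong in practice. No patient can be given a dose from a level that does not exist, and 2.1.1 and the NOTE both block the declaration. Oversight also continues: serious events go to the quality monitor and the drug supplier within 24 hours and then to the DSMC (7.3.3), DLT-period data are generally due weekly (11.5), and high-intensity monitoring applies (11.7). This stands. A reader might infer that patients would receive a wrong dose or that safety review is absent, and the documents support neither. What is missing is the specific decision step for this branch.

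Appendix 5 describes the level 1 consultation in general terms, so one could argue that it was meant for any failure at level 1. That may have been the intent. The log is not the operative text, however, and the current 4.3 attaches the clause to one branch only.

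The re-opening case is also not the same literal error. The instruction about the previous level is nested under one DLT in three, so it does not apply after none in three. The NOTE's example allows a declaration only with 0 or 1 DLT in six. What is absent there is a next step.

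The level 2 wording is largely editorial. The treatment sections name no nivolumab dose above 240 mg, so a reader can see that escalation is not meant to go further. The text still instructs otherwise.

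**Conclusion.** The point holds as a contradiction in a stated decision rule for the Phase I primary objective. Followed as written, the branch of two or more DLTs in six gives an invalid result at level 1. It conflicts with 2.1.1, with the NOTE, and with the exception written for the parallel branch. This part rests on the text alone and needs no assumed rate.

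Its size does rest on an assumption. For level 1 DLT rates of 5% to 30%, the chance of reaching the invalid instruction runs from 1.9% to 29.0%.

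Two stronger readings should be avoided. A reader might infer that the uncovered branch is simply the more likely way for level 1 to fail. That is true only below a rate of about 0.39; at 0.50 the covered branch has 50.0% against 32.8%. A reader might also infer that the gap puts Phase Ib at risk. Section 8.2.5 already makes continuation into Phase Ib conditional on 240 mg being the MTD. If level 1 fails in its initial cohorts, that condition is unmet whether or not the branch is repaired.

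The re-opening gap and the level 2 wording are related and lesser.

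**What to change.** The sponsor should reconcile four items: the branches of 4.3, the NOTE with its example, the two-level dose table, and the MTD definition in 2.1.1. After that, every possible DLT count at levels 1 and 2, including level 1 after re-opening, should lead to an outcome that exists in the plan. Which outcome applies in each case is for the sponsor to decide, and none is proposed here.

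The cost is a few sentences in 4.3, with no patients and no data.

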4.3.1 Definitions

DLT is defined as a significant adverse events (detailed below) occurring during the DLT period (first 28 days of nivolumab treatment) that is related to nivolumab. DLT will be evaluated according to CTCAE v 4.03 criteria. Delay in starting nivolumab therapy more than 2 weeks due to toxicity regardless of attribution or grade, is considered a DLT

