4.10 Patient Replacement

Any patient who signs consent but does not receive study treatment may be replaced. In addition, any study patient who receives Y-90 but discontinues prior to treatment with nivolumab can be replaced. This includes patients who cannot start nivolumab within 4 weeks of Y-90 treatment, who must come off study.

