6.2 Primary Endpoint

The primary endpoint of this study is establishing the maximum tolerated dose for the combination therapy of nivolumab and Y-90. Patients who received at least one dose of nivolumab will be considered for evaluation.

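### A toxicity delay that prevents nivolumab from starting is a DLT in 4.3.1, but 4.2.2, 4.10 and 6.2 take that patient out of the 3+3 count

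*Combined protocol and SAP*

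**What the plan says.** **DLT definition (4.3.1).** The general rule covers significant adverse events "occurring during the DLT period (first 28 days of nivolumab treatment) that is related to nivolumab". A separate sentence then adds: "Delay in starting nivolumab therapy more than 2 weeks due to toxicity regardless of attribution or grade, is considered a DLT". It does not name the day from which the two weeks run.

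**Start window (4.1, 4.2.2).** Nivolumab is planned for 7 to 14 days after Y-90. If side effects persist at day 14, "nivolumab treatment may be delayed by up to 14 additional days", which gives day 28 as the limit.

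**Replacement (4.2.2, 4.10).** Section 4.2.2 says: "If a patient is not able to start nivolumab treatment within 4 weeks (28 days), the patient should come off study and be replaced". Section 4.10 says that "any study patient who receives Y-90 but discontinues prior to treatment with nivolumab can be replaced", and adds: "This includes patients who cannot start nivolumab within 4 weeks of Y-90 treatment, who must come off study". Neither section treats toxicity differently from any other reason for not starting.

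**Who is evaluated.** Section 6.2, on the MTD, says: "Patients who received at least one dose of nivolumab will be considered for evaluation". Sections 4.4 and 6.3.1 also make a patient evaluable for toxicity from the first nivolumab dose.

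**Decision rule.** Section 2.1.1 defines the MTD as the highest dose with DLTs in fewer than 2 of 6 patients. Under 4.3, two or more DLTs in six mean that the level fails, and the level declared the MTD must have six patients treated. Under 8.2.5, the study continues into Phase Ib provided 240 mg is the MTD.

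**The concern.** The delay sentence is a deliberate widening of the DLT definition: toxicity bad enough to hold back nivolumab counts against the combination, whatever its cause or grade. The sections that govern replacement and evaluability do not recognise it. A patient who meets it can be removed, replaced and left out of the MTD evaluation by a team following 4.2.2, 4.10 and 6.2 to the letter. A team following 4.3.1 to the letter would count the same patient.

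The result at stake is the Phase I primary endpoint. With six patients per level the decision turns on a single event, and the protocol does not say which section prevails. The choice would be made after the event, when its effect on the dose is already known.

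**Working it through.** The plan states no operating characteristic for the 3+3 part, so there is no figure to reproduce. The check sets the rules against a timeline and then sizes the consequence.

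**Step 1: which patients meet the delay rule.** Day 0 is Y-90; the planned start is days 7 to 14; the limit is day 28.

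| Two weeks counted from | Delay DLT means | Patients affected |
|---|---|---|
| Day 14 (latest planned start) | no start by 14 + 14 = day 28 | only patients removed undosed |
| Day 7 (earliest planned start) | no start by 7 + 14 = day 21 | starts on days 22-28, plus those removed undosed |
| Day 0 (Y-90) | no start by day 14 | starts on days 15-28, plus those removed undosed |

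The first row fits 4.2.2 best, because its two weeks coincide with the 14 additional days allowed there. The other two rows would make DLTs of starts that 4.1 and 4.2.2 permit. On the first row every delay DLT falls in a patient who is removed without a nivolumab dose, so under 6.2 the sentence adds nothing to the count. On the other rows some delay DLTs are countable, but the longest delays still drop out.

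**Step 2: effect of one patient, with no assumed rate.** At 240 mg, suppose five dosed patients have one DLT between them and a sixth cannot start by day 28 because of toxicity.
- Counted: 1 + 1 = 2 of 6, and 240 mg fails.
- Replaced by a patient without a DLT: 1 of 6, 240 mg passes and Phase Ib opens.

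**Step 3: illustration with assumed rates.** Let p be the DLT probability in a dosed patient and d the probability that toxicity prevents a start by day 28. Neither is in the documents. A level passes with at most one DLT in six. With per-patient probability q:

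P(pass) = (1 − q)^6 + 6q(1 − q)^5

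If non-starters are replaced, q = p. If they are counted, q = d + (1 − d)p. For p = 0.10 and d = 0.10, q = 0.10 + 0.90 × 0.10 = 0.19, and P(pass) = 0.81^6 + 6 × 0.19 × 0.81^5 = 0.282 + 0.397 = 0.680. Replaced, it is 0.90^6 + 6 × 0.10 × 0.90^5 = 0.531 + 0.354 = 0.886.

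| p | Replaced (any d) | Counted, d = 5% | Counted, d = 10% | Counted, d = 20% |
|---|---|---|---|---|
| 5% | 96.7% | 89.1% | 78.8% | 55.8% |
| 10% | 88.6% | 78.8% | 68.0% | 46.4% |
| 20% | 65.5% | 55.8% | 46.4% | 30.1% |

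These are probabilities that 240 mg passes, given that the level is opened. The chance of at least one toxicity non-start among six enrolled is 1 − (1 − d)^6: 26%, 47% and 74% for d = 5%, 10% and 20%.

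**The case against.** The strongest reply is that replacement and DLT counting are separate matters. Sections 4.2.2 and 4.10 say who leaves and whose place is refilled; they do not say that a replaced patient's DLT is erased, and 4.10 is only permissive about replacement. Section 6.2 is one general line without the word *only*. Section 4.3.1 is the specific rule, and the DSMC confirms DLTs before escalation. On that view the specific rule governs and only a clarification is missing.

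Part of this stands. Replacement alone does not forbid recording the DLT, so a reader who infers that 4.2.2 or 4.10 cancels it goes too far. The exclusion comes from 6.2, supported by 4.4 and 6.3.1. Nor is it an inconsistency that the delay precedes the DLT period: the delay sentence openly departs from the general definition and is best read as an addition to it. The undefined start day is also less open than it looks, since 4.2.2 points to day 14.

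What does not stand is that the matter is therefore settled. Three sections tie evaluability to a nivolumab dose, no section says that a never-dosed patient enters the 3- or 6-patient count, and the DSMC is asked to apply the same definitions.

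A reader might also infer that the delay should not be a DLT at all, because an event before the first nivolumab dose cannot separate 80 mg from 240 mg. The documents do not support that step. Section 1.3 says that no data exist on the combination in HCC, 6.2 frames the MTD as that of the combination therapy, and the sponsor chose to count these delays whatever their cause. Dropping the rule is a trade-off for the sponsor to make, not a correction the text requires.

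**Conclusion.** The conflict is real and should be resolved. With the two weeks measured from day 14, the delay DLT arises only in patients whom the protocol removes undosed and does not include in the MTD evaluation. A toxicity event that the sponsor meant to count is lost, and the loss favours acceptance of 240 mg.

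The firm statement of size is that one patient can turn 2 of 6 into 1 of 6. That needs one other DLT at the level and a replacement patient without a DLT. The percentages rest on assumed p and d and show direction and scale only. They should not be read as evidence that such delays are common or that 240 mg would be wrongly accepted. Failure of 240 mg would also not by itself make 80 mg the MTD: 4.3 first requires six patients treated at 80 mg with at most one DLT.

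The documents do not show whether Phase I enrolment is complete. If it is, the report of the MTD should say how any such patient was handled.

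**What to change.** Keep the sponsor's rule and make the other sections agree with it:
- **4.3.1:** state that the two weeks run from day 14 after Y-90, so failure to start nivolumab by day 28 because of toxicity is a DLT.
- **4.2.2 and 4.10:** limit replacement to patients who do not start for reasons other than toxicity. State that a toxicity non-start counts as a DLT in the 3- or 6-patient decision at the assigned dose level.
- **6.2:** add these patients to the MTD evaluable set.
- **4.3:** since the MTD level needs six patients treated, say whether a counted non-starter is one of the six.
- Report the number of non-starters and their reasons to the DSMC.

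The cost is a few sentences and one item in the DSMC report. No new data are needed, because 4.9 already has the reason for discontinuation documented. The downside is that Y-90 toxicity which prevents nivolumab can make 240 mg less likely to be declared the MTD.

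If the sponsor prefers not to count these delays, it should delete the sentence from 4.3.1 explicitly and accept that such toxicity no longer bears on the MTD.
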